3.2. Study Start and End of Study Definitions

The start of the study is defined as the date the first subject signs an informed consent form (ICF). The point of enrollment occurs at the time of subject number allocation. The end of the study is defined as the date of the last subject's last assessment (scheduled or unscheduled).

3.3. Additional Groups

Following review of the safety, tolerability, and PK data, additional dose groups (where systemic exposure is not expected to exceed that stated in the dose escalation stopping criteria as detailed in [Section 3.7](#)) may be added to the study. Up to 3 further groups of 8 subjects (6 KRP-A218 and 2 placebo) in Part A and 3 further groups of 10 subjects (8 KRP-A218 and 2 placebo) in Part B may be added. The requirement for additional groups will be agreed with the Sponsor and documented in the trial master file (TMF).

3.4. Discussion of Study Design, Including the Choice of Control Groups

For Parts A and B of the study, a sequential-group, ascending dose design has been chosen for safety reasons as KRP-A218 is in the early stages of clinical development, with Part A of the study being the first time it will be administered to humans. Oral doses have been chosen for each part of the study, as this is the intended clinical route of administration. A 2-period design has been chosen for the food-effect arm, as this gives a within subject assessment of the influence of food on the PK of **CCI** [REDACTED] and so increases the power of the study for the given number of subjects.

It is the intent of Part B to dose subjects such that steady state plasma levels of **CCI** [REDACTED] are achieved and maintained for several days. Based on the available nonclinical data, it is expected that this will be achieved following 3 days of once daily dosing; however, a full review of all the available safety, tolerability, and PK data from Part A will be performed to confirm the dose regimen for Part B. If the $t_{1/2}$ of **CCI** [REDACTED] is longer than predicted by the nonclinical data, once-daily dosing may be more appropriate over 14 days (as steady state will take longer to achieve). The dose regimen will comprise no less than once every 3 days and will not exceed 3-times daily dosing. The dosing duration will not exceed 14 consecutive days of dosing.

Details of the dosing regimen and duration used for Part B of the study will be documented in the TMF. An interval of 7 to 10 days between doses of KRP-A218 in the food-effect arm in Part A is considered adequate to prevent carryover of KRP-A218 but the interval may be extended depending on the observed $t_{1/2}$ of **CCI** [REDACTED]

Parts A and B will be double-blind and placebo-controlled in order to avoid bias in the collection and evaluation of data during its conduct. Placebo has been chosen as the control treatment to assess whether any observed effects are treatment related or simply reflect the study conditions.

Continuous 12-lead ECG monitoring will be included in this study in order to explore potential KRP-A218 effects on the QT interval, with a view of supporting a potential thorough QT study waiver.

For Part C of the study, the fixed-sequence design to be used is typical for interaction studies where a relatively small number of subjects are required, because it allows intrasubject comparisons and reduces intersubject variability. Part C of the study will be open-label because the endpoints are not considered to be subjective.

KRP-A218 will be administered as single doses in Part C, as single oral dose studies are usually performed for interaction studies for compounds with linear PK as found for KRP-A218. Itraconazole is the reference potent CYP3A inhibitor recommended in the EMA guideline [16], and among those noted in the FDA draft guideline [17]. The dose level of itraconazole was selected based on achievement of clinically probable CYP3A inhibition and the typical clinical dose (200 to 400 mg daily dose) of itraconazole.

Nonclinical data suggest that CCI [REDACTED] is a CYP3A4 substrate. If a significant proportion of CCI [REDACTED] metabolism in humans indeed proceeds through CYP3A4, the administration of itraconazole will significantly inhibit the metabolism of CCI [REDACTED], resulting in an increase in exposure of CCI [REDACTED].

Conducting the study in healthy subjects mitigates the potential confounding effects of the disease state and concomitant medications.

3.4.1. Dose Interval

Following thorough review of all available nonclinical data (pharmacological and toxicological), dosing in each group in Part A will be such that 2 subjects (1 KRP-A218 and 1 placebo) will be dosed at least 24 hours before the remaining 6 subjects. After dosing the first 2 subjects on a separate day, a minimum of a 5-minute dosing interval for the remaining 6 subjects in each dose-ascending group is considered acceptable. Continuation to dose the remaining 6 subjects will be at the Investigator's discretion.

For Part B, dosing at each dose level will be such that 2 male subjects (1 KRP-A218 and 1 placebo) will receive the IMP at least 7 days before the remaining 8 subjects. After dosing the first 2 subjects, a minimum of a 5-minute dosing interval for the remaining 8 subjects in each dose-ascending group is considered acceptable. Continuation to dose the remaining 8 subjects will be at the Investigator's discretion.

3.5. Selection of Doses in the Study

Based upon nonclinical data, no clinically important off-target effects are expected within the proposed exposure range.

In the pivotal 2-week toxicity studies in rats and dogs, the NOAEL was < 5 mg/kg/day for male rats, 5 mg/kg/day for female rats, and 2 mg/kg/day for dogs (both sexes), and in a non-pivotal 2-week toxicity study in mice, the NOAEL was 10 mg/kg/day for male mice. Inflammatory cell infiltration in the lumen of the coagulating gland in male rats was observed at ≥ 5 mg/kg/day. However, this finding is not considered to be relevant to human safety because the coagulating gland is an accessory sex gland in rats, not in humans, and the finding may be species specific as no related changes were seen in the dog or mouse. Furthermore, no other reproductive organ findings were noted in rats, and no adverse effects on male reproductive performance were observed in a preliminary male fertility study in rats. No other findings were observed in male rat at dose of 5 mg/kg. The maximum recommended

starting dose (MRS) for a 60 kg subject, based on the most conservative human equivalent dose (HED) calculation among the treatment groups calculated from the most sensitive species, rat (lowest dose: 5 mg/kg/day [NOAEL not established for male rat]; HED: 48 mg/subject) is 4.8 mg/subject, including a 10-fold safety factor.^[19] KRP-A218 shows pharmacological effects in mice from 1 mg/kg/day, which is equivalent to a HED of 4.9 mg for a 60 kg subject. The proposed starting dose of 1 mg includes an extra 5-fold safety factor, compared with the MRS calculated from the 5 mg/kg/day for rats and the HED calculated from the 1 mg/kg/day for mice.

Due to the toxicity observed with respect to gastrointestinal effect that was observed in preclinical study in dogs,^[18] the lower dose escalation increments should be selected. The highest clinical dose should be set so that proposed maximum individual exposure for dose escalation studies is capped to the exposure seen in the male rats at 5 mg/kg/day. The corresponding C_{max} and AUC_{0-24h} values in male rats at the 5 mg/kg/day are 1220 ng/mL and 3930 ng·h/mL, respectively.

In a CV-B3 infected mouse model, the efficacy of CCI was observed in a dose dependent manner and CCI showed antiviral efficacy and improvement of survival rate.^[18] Significant efficacy was observed at 1, 3, and 10 mg/kg; however, the predicted therapeutic range (AUC_{0-24h}) initially selected was 276 to 988 ng·h/mL, as 988 ng·h/mL (the AUC_{0-24h} at 3 mg/kg) was lower than the exposure at the NOAEL in male rats whereas the mouse exposure at 10 mg/kg (AUC_{0-24h} of 4920 ng·h/mL) was higher than the exposure at the NOAEL in male rats. Therefore, the therapeutic range initially proposed was a conservative estimate and the optimal clinical therapeutic range may exceed the AUC_{0-24h} of 988 ng·h/mL.

Considering that the indication of KRP-A218 is HRV infection with a high risk of progressing to lower respiratory infection or other severe complications, it is necessary to achieve the expected exposure on the first day of administration. Based on the mean AUC_{0-24h} observed in Groups A1 to A3 (Part A of this study), the expected clinical therapeutic dose that covers the AUC_{0-24h} of 276 to 988 ng·h/mL on Day 1 is 2 to 8 mg (Table 4). To cover the estimated steady-state exposure of 8 mg with a single dose in this study, the mean exposure would need to be above 1730 ng·h/mL (mean $AUC_{0-24h} \times R$) based on current human PK data.

Table 4: Observed and Estimated Human Exposure at Day 1 and Steady State

Dose (mg)	Mean AUC_{0-24h} (ng·h/mL) (Day 1)	Mean $AUC_{0-24h} \times R$ (ng·h/mL) (Steady State)
1	145	NA
2*	271	434
3	388	NA
6	813	NA
8*	1080	1730

Abbreviations: AUC_{0-24h} = area under the concentration-time curve from time 0 to 24 hours; NA = not available; R = accumulation ratio.

R = 1.6 (calculated using the geometric mean half life value from 6 mg KRP-A218)

* Estimated AUC_{0-24h} values calculated based on the geometric mean AUC_{0-24h} from 6 mg KRP-A218, assuming linearity across dose.

Moreover, considering the individual AUC_{0-24h} values observed in Groups A1 to A3, it has been assumed that the maximum AUC_{0-24h} may be in the range of approximately 2-fold the mean AUC_{0-24h}. Therefore, it is considered reasonable to set the dose escalation criteria at the NOAEL equivalent exposure (maximum AUC_{0-24h} of 3930 ng·h/mL), which is approximately 2-fold of the estimated steady-state exposure at 8 mg (mean AUC_{0-24h}*R of 1730 ng·h/mL). In addition, based on safety data from this ongoing study at doses of 1 to 6 mg (Groups A1 to A3), no gastrointestinal findings of any concern have been observed.

Therefore, in this Phase 1 study, it is planned to investigate higher doses within the range up to the NOAEL (5 mg/kg in male rats: C_{max} 1220 ng/mL, AUC_{0-24h} 3930 ng·h/mL) as the maximum exposure for individuals.

Exploring these higher doses in a Phase 1 study will allow AEs to be more closely monitored than in Phase 2 or 3 studies.^[20] It will also allow the exploratory objective to collect data for concentration-QTc analysis to be more relevant as according to regulatory guidance, the QTc response should be characterised at a sufficiently high multiple of the clinically relevant exposure.^[21, 22, 23]

CCI was metabolized by CYP3A, CYP2C9, CYP2C8, and CYP2D6, and the contribution ratio of CYP3A was determined as ranging from 68.4 to 94.4%. Because of the high contribution ratio for CYP3A, co-administration of KRP-A218 with drugs that induce or inhibit CYP3A may affect the exposure of **CCI**. The dose level in Part C will be selected based on PK profile in preceding Parts A and/or B.

The proposed IMP dose levels for Parts A, B, and C are shown in [Table 5](#).

Table 5: Proposed Investigational Medicinal Product Dose Levels for Parts A, B, and C

Study Part	Group	Subject Numbers	Treatments	KRP-A218 Dose	Dietary State	Sex
Part A	A1	0101 – 0108	6 KRP-A218 2 placebo	1 mg	Fasted	Male
	A2a ^a	0109 – 0116	6 KRP-A218			
			2 placebo (2 doses)	3 mg	Fasted and Fed	Male
	A2b ^a	0117 – 0124	6 KRP-A218 2 placebo	3 mg	Fasted	Female
	A3	0125 – 0132	6 KRP-A218 2 placebo	6 mg	Fasted	Male
	A4	0133 – 0140	6 KRP-A218 2 placebo	12 mg	Fasted	Male
Part B	A5	0141 – 0148	6 KRP-A218 2 placebo	maximum dose of 24 mg	Fasted	Male
	B1	0201 – 0210	8 KRP-A218 2 placebo	X mg	Fasted/Fed ^b	Male
	B2	0211 – 0220	8 KRP-A218 2 placebo	X mg	Fasted/Fed ^b	Male

B3	0221 – 0230	8 KRP-A218 2 placebo	X mg	Fasted/Fed ^b	Male	
B4	0231 – 0240	8 KRP-A218 2 placebo	X mg	Fasted/Fed ^b	Male	
Part C	C1	0301 – 0312	12 KRP-A218 (2 doses)	X mg	Fasted/Fed ^b	Male

^a Female subjects in Group A2b will participate in Treatment Period 1 only. Male subjects in Group A2a will be administered the same treatment in both treatment periods and will be in the fasted state in Treatment Period 1 and in the fed state in Treatment Period 2.

^b The dietary state for dosing will be determined by comparing the PK data between the fed and fasted state in Group A2a.

For Part A, the planned first dose level is 1 mg. The dose level of the subsequent group will be set so that the predicted mean exposure does not exceed 5-fold the mean exposure of the previous group for predicted nonpharmacologically active dose, and 2-fold the mean exposure of the previous group for predicted pharmacologically active dose. The highest dose level will be guided by the review of safety, tolerability, and PK data from prior dose levels. In each group in Part A, predicted maximum systemic exposure (C_{max} and AUC_{0-24h}) of **CCI** in individual subjects will not exceed a C_{max} of 1220 ng/mL and/or an AUC_{0-24h} of 3930 ng·h/mL; i.e., systemic exposure will not exceed that seen in the male rat, which was the lowest systemic exposure that was seen at either 5 mg/kg/day in rats or the NOAEL of 2 mg/kg/day in dogs. Considering the predicted maximum systemic exposure and the observed maximum individual AUC_{0-24h} at 6 mg in Part A, the highest dose is estimated to be 17 mg (Table 6). Regardless of this estimate, the highest dose will be determined based on the review of the maximum AUC_{0-24h} value at the previous dose level; however, the maximum dose that will be administered in Part A will not exceed 24 mg, which is 2-fold the previous dose level.

Table 6: Estimated Human Exposure at Day 1

Dose (mg)	C_{max} (ng/mL)		AUC_{0-24h} (ng·h/mL)	
	Mean	Maximum	Mean	Maximum
6	60.3	95.7	813	1350
12*	121	191	1630	2700
17*	171	271	2300	3830

* C_{max} and AUC_{0-24h} were calculated based on geometric mean parameter values from 6 mg KRP-A218 in Part A, assuming linearity across dose.

For Part B, the dose levels, dosing regimen, and dietary status will be confirmed based on the review of all available safety, tolerability, and PK data in the preceding groups in Parts A and/or B. For all groups in Part B, selected dose levels will have a predicted mean steady-state exposure (C_{max} and AUC_{0-24h}) that does not exceed the mean exposure (C_{max} and AUC_{0-24h}) previously found generally safe and well tolerated in Part A. In addition, predicted maximum systemic exposure level (C_{max} and AUC_{0-24h}) of **CCI** in individual subjects that does not exceed the maximum exposure (C_{max} and AUC_{0-24h}) in individual subjects in the preceding groups in Part A and will not exceed a C_{max} of 1220 ng/mL and/or an AUC_{0-24h} of 3930 ng·h/mL; i.e., systemic exposure will not exceed that seen in the male rat, which was the lowest systemic exposure that was seen at either 5 mg/kg/day in rats.

For Part C, the dose level will be confirmed based on the review of all available safety, tolerability, and PK data in preceding Parts A and/or B. The actual dose level of KRP-A218 will be set so that the predicted mean exposure (C_{max} and AUC_{0-24h}) of CCI on co-administration of itraconazole will not exceed the mean exposure (C_{max} and AUC_{0-24h}) previously found generally safe and well tolerated in Part A and in addition, predicted maximum systemic exposure level (C_{max} and AUC_{0-24h}) of CCI on co-administration of itraconazole in individual subjects does not exceed the maximum exposure (C_{max} and AUC_{0-24h}) in individual subjects in Part A and will not exceed a C_{max} of 1220 ng/mL and/or an AUC_{0-24h} of 3930 ng·h/mL; i.e., systemic exposure will not exceed that seen in the male rat, which was the lowest systemic exposure that was seen at either 5 mg/kg/day in rats.

The actual dose levels will be determined based on emerging data.

Details of all doses administered in Parts A to C of the study will be documented in the TMF.

3.6. Dose Escalation

Doses will be administered in an escalating manner following satisfactory review by the Sponsor, Investigator, and Labcorp Drug Development Medical Monitor of the safety and tolerability data (up to 48 hours post last dose) and plasma PK data (up to 24 hours post last dose) from the previous lower dose level. Doses may be reduced and may be lower than the starting dose. There will be a minimum of 6 days between dose escalations to allow sufficient time for an adequate safety review.

Dose escalation in both Parts A and B will only occur if data from a minimum of 6 subjects have been reviewed from the previous lower dose group, such that data from a minimum of 4 subjects who have received KRP-A218 will be used to make the dose escalation decision.

The justification for this is as follows:

- Based upon nonclinical data, no clinically important off-target effects are expected within the proposed dose range.
- A minimum of 4 subjects receiving the active drug is considered sufficient to characterise the safety profile and PK response to KRP-A218.

Between each dose escalation, the Investigator will review all available data in a blinded manner to ensure it is safe to proceed with the planned dose escalation. An interim safety report, summarising results from all available safety assessments, will be sent to the Sponsor and Labcorp Drug Development Medical Monitor prior to the start of each successive group. Any clinically significant results will be discussed with the Sponsor before dose escalation continues. Interim PK data will also be reviewed in terms of dose escalation and to confirm that the study design remains appropriate. In the event of a disagreement between Sponsor and Investigator on the dose escalation decision, the decision of the Investigator will be upheld.

3.7. Dose Escalation Stopping Criteria

The study will be halted if 1 or more subjects experience an SAE that is considered to be related to IMP or 2 or more subjects in the same group experience severe AEs that are

considered to be related to IMP. If, following an internal safety review, the Sponsor deems it appropriate to restart the study, this can be done following approval of a substantial protocol amendment.

For both Parts A and B, a consultation between the Investigator, Sponsor, and Labcorp Drug Development Medical Monitor will be held prior to dosing the next group. Dose escalation will stop if:

- Clinically relevant signs or symptoms of similar nature occur in 2 or more subjects in a group that, in the opinion of the Investigator, warrant stopping of dose escalation. In particular, the Investigator (or designee) should carefully monitor signs or symptoms below:
 - symptoms such as inappetence, abdominal distension, abdominal discomfort, abdominal pain, nausea and vomiting
 - signs/findings such as abdominal tenderness and decreased or absent peristaltic sounds
 - abnormal faeces such as diarrhea, hematochezia, and melena.
- Inappetence, abdominal distension, abdominal discomfort, abdominal pain, nausea and vomiting that prevent subjects from eating a meal on 3 or more occasions on 2 consecutive days in 1 or more subjects in a group.
- Diarrhea, defined as 7 or more episodes, rated as ≥ 5 on the Bristol Stool Chart, in 1 day for 2 consecutive days in 1 or more subjects in a group.
- Hematochezia and melena with visible blood that are considered to be caused by gastrointestinal bleeding in 1 or more subjects in a group.
- Clinically significant increases in liver function tests compared to baseline measurements, defined as AST, ALT, ALP, and/or γ -GTP $\geq 3 \times$ the upper limit of normal (ULN) and/or T-Bil $\geq 2 \times$ ULN (confirmed with repeat testing) in 2 or more subjects in a group.
- Maximum systemic exposure level of CCI [REDACTED] in individual subjects in the next group predicted to exceed a C_{max} of 1220 ng/mL and/or an AUC_{0-24h} of 3930 ng \cdot h/mL.

The dosing status of an individual subject may be unblinded to reviewers of the safety data if necessary for safety reasons or if pertinent to dose escalation decisions. The unblinded status will be kept to a minimum number of reviewers, based on pertinence to their role and relevant task. Further information on blinding can be found in [Section 5.4](#).

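### Does the lack of a stated prediction method in Protocol Section 3.7 leave the PK stopping criterion open to two conflicting readings?

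*Protocol*

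**What the plan says.** The only pharmacokinetic item in the Section 3.7 list stops escalation if the maximum exposure "in individual subjects in the next group predicted to exceed a C_{max} of 1220 ng/mL" and/or an AUC0-24h of 3930 ng·h/mL. It states no method and gives no cross-reference for the prediction.

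Section 3.5 bears on that prediction in three places:

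- When arguing for the level of the cap, it says the individual maximum AUC0-24h "may be in the range of approximately 2-fold the mean".
- Before Table 6 it starts from what was seen at 6 mg ("Considering the predicted maximum systemic exposure and the observed maximum individual" AUC0-24h) and concludes that "the highest dose is estimated to be 17 mg".
- It then sets that figure aside: "Regardless of this estimate, the highest dose will be determined based on the review of the maximum" AUC0-24h at the previous dose level, with 24 mg as an absolute ceiling for Part A.

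The Table 6 footnote says the Cmax and AUC0-24h entries "were calculated based on geometric mean parameter values from 6 mg KRP-A218 in Part A, assuming linearity across dose".

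On the origin of the cap, Section 3.5 says it is reasonable to "set the dose escalation criteria at the NOAEL equivalent exposure" and that "it is planned to investigate higher doses within the range up to the NOAEL", meaning 5 mg/kg in male rats. Section 1.2 puts the male-rat NOAEL below 5 mg/kg/day. An earlier part of Section 3.5 repeats this and adds that no male-rat NOAEL was established.

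**The concern.** This is a first-in-human study, and a stopping rule that depends on a prediction should let two people with the same data reach the same answer. Section 3.7 alone does not. A reader who turns to Section 3.5 finds a 2-fold multiplier and a table that implies a smaller one, and the two fall on opposite sides of the AUC cap at the protocol's own 17 mg estimate. If the multiplier were a free choice, so would be the decision for Group A5, the last planned single-dose group.

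The label adds to the unease. Calling the cap a NOAEL exposure, when the same protocol says the male-rat NOAEL lies below that dose, could suggest a safety margin that was not shown. The cap values also carry no study day, and the sentence justifying them for Parts B and C breaks off before the comparison with dogs.

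**Working it through.** **Inputs.** From Table 6, at 6 mg: AUC0-24h mean 813 and maximum 1350 ng·h/mL; Cmax mean 60.3 and maximum 95.7 ng/mL. From Section 3.7: caps of 3930 ng·h/mL and 1220 ng/mL. Scaling is linear in dose, as Table 6 assumes.

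**Reproducing Table 6 at 17 mg.**
- Mean AUC0-24h: 813 × 17/6 = 2304 (shown as 2300).
- Maximum AUC0-24h: 1350 × 17/6 = 3825 (shown as 3830).
- Maximum Cmax: 95.7 × 17/6 = 271 (shown as 271).

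The Maximum column therefore comes from the observed maxima. The footnote's geometric means produce only the Mean column.

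**Maximum-to-mean ratio at 6 mg.** AUC0-24h: 1350/813 = 1.66. Cmax: 95.7/60.3 = 1.59. At 17 mg the AUC cap is reached at a ratio of 3930/2304 = 1.71.

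**The two routes**, extrapolated from 6 mg, with 1350/6 = 225 per mg for the scaled maximum and 2 × 813/6 = 271 per mg for twice the mean:

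| Dose | Scaled maximum | Twice the mean | Against 3930 |
|---|---|---|---|
| 12 mg | 2700 | 3252 | both below |
| 17 mg | 3825 | 4607 | one below (0.973), one above (1.172) |
| 24 mg | 5400 | 6504 | both above |

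The cap is reached at 3930/225 = 17.5 mg on the first route and 3930/271 = 14.5 mg on the second. These are arithmetic crossings, not dose proposals. Cmax does not bind: the scaled maximum is 271 ng/mL at 17 mg and 95.7 × 24/6 = 383 at 24 mg, against 1220.

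**What the 2-fold figure does.** Section 3.5 compares the cap with the estimated steady-state mean at 8 mg, 1730 ng·h/mL. Twice that is 3460, below 3930. The same passage describes 3930/1730 = 2.27 as approximately 2-fold, so the multiplier is not meant to be exact. It is not applied to any Part A dose.

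**Study day.** In Tables 1 and 2, at 5 mg/kg/day in rats and 2 mg/kg/day in dogs (male rat, female rat, male dog, female dog):
- Day 14: lowest Cmax = min(1220, 1600, 1450, 1350) = 1220; lowest AUC0-24h = min(3930, 4780, 9340, 8500) = 3930.
- Day 1: lowest Cmax = min(962, 1370, 1450, 918) = 918; lowest AUC0-24h = min(3610, 4910, 8020, 6000) = 3610.

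The cap values are the Day 14 figures, and the claim that they are the lowest holds for both measures on that day. For AUC0-24h, the only measure near its cap, the male rat is lowest on both days. Day 14 is 3930/3610 = 1.089 times Day 1.

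**The case for a change.** The strongest counter-argument is that the Section 3.5 sentence on the previous dose level speaks only of the highest Part A dose, whereas Section 3.7 applies to Parts A and B, and Section 3.3 ties any added groups to the same limits. Reviewing a maximum is also not a formula. Nothing says how an individual maximum is predicted at steady state, where Table 4 uses an accumulation ratio of 1.6. When A5 is set from 12 mg data, the two routes agree only if the observed 12 mg maximum-to-mean ratio happens to be 2.

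The observed maximum may also rest on as few as four active subjects. If AUC0-24h is assumed lognormal and the 27.9% CV at 6 mg in Table 3 is read as a geometric CV, about 2.6% of individuals would exceed 3930 at 17 mg, and the chance of at least one among six active subjects would be about 14%.

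Much of this is factually right. Section 3.7 would read better with a cross-reference, and a maximum from a few subjects is a noisy predictor. It does not follow that the rule is undetermined. For Part A, Section 3.5 says which observation governs, Table 6 shows the scaling, and Sections 3.6 and 3.7 require PK review and a three-party consultation before the next group. Section 3.5 separately limits the step in predicted mean exposure to 2-fold at pharmacologically active doses. In Parts B and C, predicted mean exposure may not exceed that found generally safe and well tolerated in Part A, and predicted individual maxima may not exceed those seen in Part A. If Part A maxima stay below the cap, those limits are the tighter ones.

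The label conflict is real, but it conceals nothing. Section 3.5 discloses the male-rat finding and explains why it is considered not relevant to humans. The sentences that set the cap describe it as the exposure at 5 mg/kg/day in male rats, and Section 3.7 does not use the word NOAEL.

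**Conclusion.** No change to the plan follows. The missing method is a gap that Section 3.5 fills for Part A, and the 2-fold figure is background to the cap, not a rival rule. The opposite-sides result is confined to about 14.5 to 17.5 mg when extrapolating from 6 mg, and it attaches to an estimate the protocol declares non-binding. The actual A5 decision rests on the 12 mg data.

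The other points are clerical: a footnote that describes only the Mean column, a NOAEL label at odds with Sections 1.2 and 3.5, cap values without their Day 14 label, and a sentence for Parts B and C that stops short of the dog comparison given in full for Part A. These passages must be reconciled with one another as text, and the cap and doses remain the sponsor's decision. Reconciling them would change no cap value, escalation decision or SAP analysis.

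This conclusion assumes that exposure stays roughly linear in dose, as Table 6 does, and that the escalation review uses the previous-level maximum as Section 3.5 states. If the sponsor meant the 2-fold multiplier to be the prediction rule, the 17 mg estimate would not fit under the cap, but nothing in the text gives it that role.
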